To achieve between-group comparability, the randomization will be stratified (yes or no) for current use of concomitant medication(s) that reduce the frequency of migraine episodes.

At Visit 2, patients will be provided with study drug to treat a single migraine attack. Site personnel will confirm that they have located the correct investigational product by entering a confirmation number found on the investigational product into the IWRS before patients leave the site at Visit 2.

7.2.1. *Selection and Timing of Doses*

The actual time of dose administration will be recorded in the patient's eDiary. Patients will be instructed to take 3 tablets as the treatment for a new migraine attack, along with the following instructions:

- The migraine must be at least of moderate or severe severity.
- The migraine must be treated within 4 hours of pain onset.
- No prior analgesic or acute migraine treatment within 24 hours of study drug administration has been taken to treat the current migraine attack.

7.2.1.1. *Rescue/Recurrence Medication*

Rescue medication will be permitted after completion of the 2 hour assessments if the migraine does not respond with study drug (patient is not headache pain free). If the migraine does not respond within 2 hours, a rescue dose of NSAIDs, acetaminophen, and/or antiemetic drugs may be taken after completion of the 2 hour assessments of the study drug dose. Triptans, ergots, opioids and barbiturates MUST NOT be used for rescue medication within 24 hours of study drug administration.

If the migraine responds within 2 hours (headache becomes pain free) but then recurs after 2 hours, a dose of NSAIDs, acetaminophen, and/or antiemetic drugs may be taken after completion

of the 2 hour assessments of the study drug dose. Triptans, ergots, opioids and barbiturates MUST NOT be used for recurrence medication within 24 hours of study drug administration.

The use of rescue and recurrence medication details will be recorded in the paper diary.

Figure LAIH.2 illustrates allowance period of these restricted rescue and recurrence medications.

[figure not shown]

Figure LAIH.2. Allowance of restricted rescue/ recurrence medications.

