10.3.7. Subgroup Analyses

Subgroup analyses will be conducted using the following patient groups:

- Patients at risk of cardiovascular disease.
- Patients who use triptans within 3 months of screening.
- Patients who fail the most recent triptan at any time before screening.
- Patients who use migraine prevention therapy during the study.

The following tables, figures and listings will be created for the subgroup analyses:

- Demographics for the mITT.
- Efficacy analyses (pain free at 2 hours) for the mITT.
- Efficacy analyses (pain relief at 2 hours and MBS at 2 hours) for the mITT.
- Safety analyses (TEAE) for the SP.

Further detail (and other subgroup analyses, if any) will be specified in the SAP.

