- For Kaplan-Meier analysis, corresponding figures will be created. Quartiles and rates, along with 95% CIs, were estimated using the Kaplan-Meier method. Corresponding 95% CIs were estimated using the methods of Brookmeyer and Crowley, and Greenwood, respectively.
- When baseline usage of preventive medications to reduce the frequency of migraine (Yes/No) is included in a statistical model, it is based on CRF, not IWRs.
- Efficacy analyses are based on eDiary data, unless otherwise specified.
- Comorbid condition is based on Visit 1.
- When median is used for subgroup analysis (e.g. SUB4, body weight), the median is based on mITT population.

We will use the following analysis population rules unless otherwise specified (see population definitions in Section [5.3](#)):

- Protocol deviation summary will be based on all randomized and mITT/ITT.
- Demographics and Baseline characteristics will be based on mITT/ITT/safety population (SP).
- Efficacy analyses [T1], [T2], [T3], and MBS will be based on mITT/ITT/per-protocol set (PPS).
- Other efficacy and health outcome will be based on ITT.
- Safety analyses (e.g., AE, laboratory assessments/vital signs), medication, and treatment compliance/eDiary compliance will be based on SP.

When continuous variables, including change from baseline scores, is summarized using descriptive statistics, it will show n (number of subjects with available data), mean, median, standard deviation, minimum, and maximum.

Minimum and maximum values will be presented to the same precision as the raw data. Mean and median will be presented to one more decimal place than the raw data. Standard deviation will be presented to two more decimal places than the raw data. P-values will be presented to three decimal places.

Categorical variables will be summarized using counts and percentages. Unless otherwise specified, percentages will be calculated using the numbers of subjects in the summarized

population in each treatment group as denominators. Percentages will be presented with a precision of 1 digit after the decimal.

Observations collected prior to dosing will serve to determine a baseline measurement; the latest available measurement prior to dosing will be used as the baseline. For data collected by eDiary, the baseline values will be the Hour-0 assessment times identified in the eDiary.

SAS® software (version 9.2 or higher) will be used to perform most or all statistical analyses.

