5.8. Subgroup Analysis

Subgroup analysis is summarized in [Table LAIH. 5.6](#).

- For efficacy analyses based on proportion, the logistic regression used in [T1] will be applied to each subgroup separately. The model term includes treatment and baseline usage of preventive medications to reduce the frequency of migraine (Yes/No). The odds ratio (relative to placebo), its 95% confidence interval, and p-value will be calculated based on this model.
- For efficacy analyses based on proportion, additional logistic regression will be used. The model term includes treatment, baseline usage of preventive medications to reduce the frequency of migraine (Yes/No), subgroup, and treatment-by-subgroup interaction. The p-value for treatment-by-subgroup interaction will be displayed. The level of significance for interaction (2-sided test) is defined as 0.05 (See Section [5.4](#)).
- For efficacy analyses based on continuous variables, ANOVA will be used for each subgroup separately. The model includes treatment and baseline usage of preventive medications to reduce the frequency of migraine (Yes/No). Change from baseline and p-values for treatment comparison will be calculated.
- For efficacy analyses based on continuous variables, additional ANOVA will be used for The model includes treatment, baseline usage of preventive medications to reduce the frequency of migraine (Yes/No), subgroup, and treatment-by-subgroup interaction. The p-value for treatment-by-subgroup interaction will be displayed. The level of significance for interaction (2-sided test) is defined as 0.05.

Table LAIH. 5.6 Subgroup Analysis

ID	Type	Analysis population [Note 1]	Dmg	PF/PR/ MBS/ Disa. at 2h	PGI-C at 2h/24h, Satisf. at 48 h	TEAE by PT	Other Analysis
SUB1	Triptan responder vs. insufficient responder (based on the most recent triptan experience)	mITT and patients who has triptan experience in lifetime	O		O	O	[1] PF/PR/MBS/disability time course (up to 48 hours) [2] EQ-5D-5L at 24h [3] Triptan detail summary at baseline

ID	Type	Analysis population [Note 1]	Dmg	PF/PR/ MBS/ Disa. at 2h	PGI-C at 2h/24h, Satisf. at 48 h	TEAE by PT	Other Analysis

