CVRF9: Family (Parents, Grandparents, and siblings) history of CVD (Yes for Coronary artery disease, Cardiovascular disorder, or Cerebrovascular disorder in eCRF “Associate Person Medical History: Special Interest”)

SUB13: Patients who use migraine prevention therapy during the study.

Note: This is based on CRF, not IWRS.

Group 1: Patients who use migraine prevention therapy

Group 2: Otherwise.

SUB14: Migraine with aura (Medical History) (with/without)

Group 1: Patients having migraine with aura in medical history.

Group 2: Otherwise

SUB15: Gender

Group 1: Male

Group 2: Female

SUB16: Age

Group 1: Age <=median

Group 2: median < Age

SUB17: Rescue or Recurrence Medication Use

Patients who use rescue or recurrent medication at specific time (0 hour is dosing time) defined below.

Group 1: 0 hour <= medication use <=2 hour

Group 2: 2 hours < medication use <=24 hour

Group 3: 24 hours < medication use <=48 hours

Note: Patients can be in multiple groups.

SUB18: Triptan users 3 months prior to informed consent (yes/no)

Group 1: Patients who used at least one triptan within 3 months of informed consent.

Group 2: Otherwise

SUB19: TEAE-Somnolence regardless of causality (with/without)

Group 1: Patients who has at least one TEAE-Somnolence regardless of causality

Group 2: Otherwise.

SUB20: Triptan naïve vs. experienced (ever)

Group 1: Triptan experienced = patients who has triptan experience in lifetime

Group 2: Otherwise.

SUB21: Pain Freedom over Time

At each postbaseline time point, subgroup is defined as

Group 1: Patients who achieved pain freedom at the time point.

Group 2: Otherwise.

Percent of patients with no disability by pain freedom (yes versus no) over time will be displayed. There is no statistical test. Missing data were excluded from the analysis at each time point. For patients who took rescue medication, data were also excluded.

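### SUB13 defines preventive users by use during the study with no cut-off at dosing, so post-outcome information can enter the one stratified subgroup; anchor it at baseline

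*SAP*

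**What the plan says.** SAP 5.8 lists "SUB13: Patients who use migraine prevention therapy during the study" and adds "Note: This is based on CRF, not IWRS". Protocol 10.3.7 names the same subgroup: "Patients who use migraine prevention therapy during the study". Neither gives a visit or a time window.

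Preventive use is also the trial's only stratification factor. Protocol 7.2 states that "the randomization will be stratified (yes or no) for current use of concomitant medication(s) that reduce the frequency of migraine episodes".

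For the models, SAP 5.8 says that "the logistic regression used in [T1] will be applied to each subgroup separately", with treatment and baseline preventive use as terms. It adds an interaction model: "The model term includes treatment, baseline usage of preventive medications to reduce the frequency of migraine (Yes/No), subgroup, and treatment-by-subgroup interaction". No exception is made for SUB13. SAP 5.4 says of the preventive-use covariate that "it is based on CRF, not IWRs", so the covariate and the subgroup share a source.

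**The concern.** A subgroup compared on a treatment effect should be fixed before the outcome is known. The SUB13 wording covers the whole study, including the 3 to 28 days between dosing and Visit 3. A patient whose attack did not respond may be more likely to be started on a preventive. That patient would move from the non-user to the user group because of the 2-hour result.

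What is at stake is the reading of one protocol-specified subgroup. It is also the subgroup for which a clean baseline definition is easiest to obtain, because the randomisation was stratified on that factor.

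A second, smaller matter is that the general SAP 5.8 models already contain baseline preventive use. In SUB13 that term nearly repeats the subgroup itself.

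**Working it through.** **1. Can post-dose use enter?** Setting the sections side by side:
- Protocol 7.7: medication use is recorded from Visit 1 through Visit 3. Protocol 5.1: Visit 3 is 3 to 28 days after the treated attack.
- SAP 5.3: mITT requires a postdose assessment, a recorded dosing time, moderate or severe baseline pain, and dosing within 4 hours. Later withdrawal does not remove a patient.
- SAP 5.5.4: medications taken from 48 hours after dosing to the end of the study are tabulated, with preventives as their own group. The data that SUB13 could pick up are therefore collected and classified.
- SAP 5.5.1, Note 2 states that subjects who discontinue have not taken study treatment. The SAP thus does not foresee a dosed patient who starts a preventive and is withdrawn.
- Elsewhere in SAP 5.8 there are anchors. Valproic acid, lomerizine and amitriptyline use under SUB2 are tied to Visit 2, and most cardiovascular risk factors to Visit 1.

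The wording therefore allows it. Only starters can change group; a baseline user who stops has still used a preventive during the study.

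**2. Size.** The plan gives no figure for SUB13. Inputs from SAP 5.2 are pain-free rates of 21.3% (placebo) and 38.8% (200 mg), with mITT n of 190 and 163. As a check on these inputs, the stated power was recomputed: T1 95.1% (stated 93.6%), T2 94.9% (94.9%), T3 92.3% (91.2%), all three 86.9% (85.6%). Each is within 2 points, and none is in dispute.

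Assumptions not in the documents: 25% baseline users, the same response rates in users and non-users, and a fraction s of non-responding non-users who start a preventive before Visit 3.

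User-group rate = (users × p) / (users + movers), where movers = non-users × (1 − p) × s. At s = 5%:
- Placebo: users 47.5; movers 142.5 × 0.787 × 0.05 = 5.6; rate 10.1/53.1 = 19.1%.
- 200 mg: users 40.75; movers 122.25 × 0.612 × 0.05 = 3.7; rate 15.8/44.5 = 35.5%.

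| s | Difference in users (points) |
|---|---|
| 0% | 17.5 |
| 2% | 17.1 |
| 5% | 16.5 |
| 10% | 15.5 |

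In non-users the difference rises to 17.9 points at s = 5%. The standard error in users is √(0.213 × 0.787/47.5 + 0.388 × 0.612/40.75) = 9.7 points, a 95% half-width of about 19.

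**3. Odds ratio, the estimate SAP 5.8 reports.** The true value is (0.388/0.612)/(0.213/0.787) = 2.34. Moving non-responders multiplies the user group's non-responder count by 1 + 3s (non-users are three times the users). With equal s in both arms the factor cancels and the odds ratio stays at 2.34 in both groups. With s = 5% on placebo and 2% on 200 mg:
- Users, no covariate: 2.34 × 1.15/1.06 = 2.54.
- Non-users: 2.34 × 0.95/0.98 = 2.27.

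With the covariate kept, it singles out the movers, who are all non-responders here. Its coefficient diverges, the user odds ratio returns to 2.34, and non-users remain at 2.27.

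**4. The repeated covariate.** Design matrices were built at 190:81:190:163 with assumed user shares of 20%, 35% and 50%.
- SUB13 equal to baseline use: each by-group model has rank 4 of 5 (covariate constant), and the interaction model has rank 8 of 9 (covariate identical to subgroup).
- In simulated data at 35% users, the 200 mg log odds ratio is 0.828 in users and 0.472 in non-users with or without the extra term. The interaction model's log-likelihood is −363.924 both ways.
- With 1 to 14 of 624 patients reclassified, the interaction model is 9 of 9 and the user model 5 of 5, with the covariate resting only on those patients. The non-user model stays at 4 of 5.

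**The case against.** The strongest reply is that the protocol already fixes preventive use. Exclusion 21 bars starting or changing a preventive within 3 months before Visit 1, and Protocol 7.7 and 8.2 call for withdrawal of anyone who needs to start or change one afterwards. For a compliant patient, use during the study is use at baseline. The window is often short as well, since sites are to encourage an early Visit 3. This stands, and it is why the effect should be rare. It does not close the gap, because a patient withdrawn after dosing remains in mITT.

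A reader might infer that SUB13 does use post-dose information and is biased. The documents show only that it can. The user share and start rates above are assumptions, and the shift they produce is small beside the sampling error.

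A reader might also infer that the duplicated covariate spoils the model. It does not. Where it is constant or aliased it simply cannot be estimated. SAP 5.8 asks for odds ratios, confidence intervals, p-values and an interaction p-value, and none of these changes when the term is dropped. Nor do the two issues hold in full together: exact aliasing in the interaction model requires that nobody is reclassified.

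**Conclusion.** The point holds in a limited form. SUB13 has no cut-off at dosing, so a dosed mITT patient who starts a preventive before Visit 3 can be counted as a user on post-outcome information. Under the assumed 25% user share and start rates of 2% to 10%, the difference in users shifts by 0.4 to 2.0 points. The odds ratio moves only if starting differs by arm. SUB13 is one of 21 subgroups, has no multiplicity adjustment, and does not bear on T1, T2 or T3. This is a small improvement available at no cost, not an error in the trial's main conclusions.

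**What to change.** In SAP 5.8, define SUB13 as CRF-recorded use of a migraine preventive at baseline (Visit 2, before dosing), using the same CRF variable as the model covariate. The randomisation stratum is not the right substitute, because the SAP deliberately takes this variable from the CRF rather than the IWRS.

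As tidying, and only together with that definition, omit the preventive-use covariate from the SUB13 models. The by-group models then have rank 4 of 4 and the interaction model 8 of 8, with the same treatment and interaction estimates. Dropping the covariate while keeping the present definition would be a step back, as the 2.54 in the differential-start example shows.

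The cost is a line or two of SAP wording and no new data. Protocol 10.3.7 leaves subgroup detail to the SAP.

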5.9. CCI

For more details of [T1], [T2], and [T3], see Section [5.6.1](#).

5.10. Unblinding Plan

During the study, some members are unblinded ([Table LAIH. 5.8](#)). These members will not be allowed to join meetings which may affect the other members' blind condition, such as trial level safety review (TLSR) and data review meetings.

Table LAIH. 5.8 Unblinded Members through LAIH Study

Role	Reason	Data source for unblinding
Product Delivery personnel	To provide and manage Clinical trial materials	e-CTS
Unblind Case Manager	To report SAE with unblinded information to EU authority	e-CTS
Clinical Laboratory	To manage and track sample shipping	CLRM

Abbreviations: CLRM = Clinical Laboratory Results Modernization; e-CTS = Enhanced Clinical Trials System; EU = European Union; SAE = Serious Adverse Event.

5.11. Clinical Trial Registry Analyses

Additional analyses will be performed for the purpose of fulfilling the Clinical Trial Registry (CTR) requirements. These analyses will be the responsibility of the Sponsor.

Analyses provided for the CTR requirements include the following:

A summary of AEs will be provided as a dataset which will be converted to an XML file. Both SAEs and ‘Other’ AEs are summarized: by treatment group, by MedDRA PT (preferred term).

- An AE is considered ‘Serious’ whether or not it is a TEAE (Definitions of AE and TEAE are in Section 5.7.1).
- An AE is considered in the ‘Other’ category if it is both a TEAE and is not serious. For each SAE and ‘Other’ AE, for each term and treatment group, the following are provided:
 - the number of participants at risk of an event
 - the number of participants who experienced each event term
 - the number of events experienced.
- AE reporting is consistent with other document disclosures for example, the CSR, manuscripts, and so forth.

Appendix 1. eDiary Assessments

	Visit 2	Predose	Postdose								
			0h	0.5h	1h	1.5h	2h	3h	4h	24h	48 h
eDiary Assessment for attacks treated with study drug											
Headache severity (0 = no pain, 1 = mild pain, 2 = moderate pain, and 3 = severe pain)		X	X	X	X	X	X	X	X	X	X
Presence or absence (yes or no) of accompanying symptoms: photophobia, phonophobia, nausea, and vomiting		X	X	X	X	X	X	X	X	X	X
Select from the accompanying symptoms present (nausea, phonophobia or photophobia only) which one is the most bothersome		X									
Time at which headache relief became meaningful											X
Time at which they become headache pain free											X
MQoLQ										X	
EQ-5D-5L	X	X								X	
Disability		X	X	X		X				X	
PGI-C						X				X	
Treatment Satisfaction											X

Abbreviations: eDiary = electronic diary; EQ-5D-5L = EuroQol 5 Dimension 5 Level; h = hours; MQoLQ = 24-Hour Migraine Quality of Life Questionnaire; PGI-C = Patient Global Impression of Change.

PPD
